### 5.3 Guidelines for Dose Modification: Non-hematologic Toxicities

Adverse Event	Grade	ADCT-502 Management Guideline
Infusion-related reactions	1	
The infusion rate may be decreased by 50% or temporarily interrupted for up to 6 hours to permit resolution of the event.
 
Acetaminophen (paracetamol) and/or H1- and H2-receptor antagonists (e.g., diphenhydramine, ranitidine) may be administered for symptomatic treatment per institutional standard at the discretion of the Investigator.
 
Consider premedication (e.g., secondary prophylaxis) with acetaminophen (paracetamol) and/or H1- and H2-receptor antagonists at least 30 minutes prior to start of subsequent doses.

	2	
Interrupt ADCT-502 infusion for up to 6 hours to permit resolution of the event. If the event resolves within 6 hours, resume ADCT-502 infusion at 50% of the prior infusion rate. Acetaminophen (paracetamol) and H1- and H2-receptor antagonists (diphenhydramine and ranitidine) should be administered for symptomatic treatment. If the patient experiences chest tightness, dyspnea, or shortness of breath, IV methylprednisolone 100 mg (or the equivalent) should be administered.
 
If the event resolves within 6 hours and requires IV steroid treatment, pre-medicate (e.g., secondary prophylaxis) with acetaminophen (paracetamol), H1- and H2-receptor antagonists (e.g., IV diphenhydramine, and IV ranitidine), and IV methylprednisolone 100 mg (or the equivalent) at least 30 minutes prior to start of subsequent doses.
 
If the event resolves within 6 hours and did not require IV steroid treatment, pre-medication (e.g., secondary prophylaxis), at least 30 minutes prior to start of subsequent doses may be considered.

Adverse Event	Grade	ADCT-502 Management Guideline
Hypersensitivity and infusion-related reactions	3	Permanently discontinue ADCT-502 unless AE resolves within 24 hours after onset (with or without clinical management). Manage severe infusion-related reactions per institutional guidelines (i.e., treatment with IV diphenhydramine, IV ranitidine, and IV glucocorticoids).  Intramuscular epinephrine should be used after failure of other therapeutic options.
Hypersensitivity and infusion-related reactions	4	Permanently discontinue ADCT-502.
Transaminase (AST/ALT) Abnormalities	2	No dose modification is required.
	3	Hold ADCT-502 until improvement to $\leq$ Grade 1 or Baseline. Up to 1 dose of ADCT-502 may be skipped to permit improvement.  First Occurrence:  If improvement to $\leq$ Grade 1 or Baseline occurs prior to next scheduled dose, continue ADCT-502 at the original assigned dose at the next scheduled treatment cycle.  If improvement to $\leq$ Grade 1 or Baseline within 21 days from last scheduled (but missed) ADCT-502 dose, continue ADCT-502 at 1 dose level below the original assigned dose in subsequent treatment cycles. If improvement to $\leq$ Grade 1 or Baseline does not occur within 21 days from the last scheduled (but missed) ADCT-502 dose, permanently discontinue ADCT-502.  Second Occurrence:  If improvement to $\leq$ Grade 1 or Baseline within 21 days from last scheduled (but missed) ADCT-502 dose, then continue ADCT-502 at 2 dose level below the original assigned dose in subsequent treatment cycles. If improvement to $\leq$ Grade 1 or Baseline does not occur within 21 days from the last scheduled (but missed) ADCT-502 dose, permanently discontinue ADCT-502.  Third Occurrence:  Permanently discontinue ADCT-502.
Hyperbilirubinemia	2	Hold ADCT-502 until improvement to $\leq$ Grade 1 or Baseline. If improvement to $\leq$ Grade 1 or Baseline occurs prior to next scheduled dose, continue ADCT-502 at the original assigned dose at the next scheduled treatment cycle.  First Occurrence:  If improvement to $\leq$ Grade 1 or Baseline within 21 days from last scheduled (but missed) ADCT-502 dose, continue ADCT-502 at 1 dose

Adverse Event	Grade	ADCT-502 Management Guideline
		
level below the original assigned dose in subsequent treatment cycles. If improvement to <math>\leq</math> Grade 1 or Baseline does not occur within 21 days from the last scheduled (but missed) ADCT-502 dose, permanently discontinue ADCT-502.
 
Consider close monitoring as needed.
 
Second occurrence:
 
Permanently discontinue ADCT-502
 
Permanently discontinue ADCT-502 for any case meeting Hy's Law criteria.

	3	
Hold ADCT-502 until improvement to <math>\leq</math> Grade 1 or Baseline. Up to 1 dose of ADCT-502 may be skipped to permit improvement.
 
First occurrence:
 
If improvement to <math>\leq</math> Grade 1 or Baseline occurs prior to next scheduled dose, continue ADCT-502 at the original assigned dose at the next treatment cycle. If improvement to <math>\leq</math> Grade 1 or Baseline occurs within 21 days from the last scheduled (but missed) ADCT-502 dose, continue ADCT-502 at 1 dose level below the original assigned dose in subsequent treatment cycles. If improvement to <math>\leq</math> Grade 1 or Baseline does not occur within 21 days from last scheduled (but missed) ADCT-502 dose, permanently discontinue ADCT-502.
 
Second occurrence:
 
Permanently discontinue ADCT-502.

Changes in LVEF	1-4	See Table 3

## 5.4 Guidelines for Dose Modifications: Left Ventricular Dysfunction

ADCT-502 should be discontinued in any patient who develops confirmed congestive heart failure (CHF) (i.e., Grade  $\geq 3$  left ventricular systolic dysfunction as defined by NCI CTCAE version 4.0). CHF should be treated and monitored according to standard medical practice.

If ADCT-502 is withheld due to clinically significant (e.g.,  $\geq$  Grade 3 or per investigator judgement) left ventricular cardiac dysfunction and treatment is then resumed, left ventricular ejection fraction (LVEF) measurement must be repeated after every cycle for the next 2 cycles and then every 3 cycles and at End of Treatment (EOT).

ADCT-502 must be discontinued in all patients for whom a drop of LVEF to below 40% is documented (unless it is not confirmed with a repeat assessment within 21 days).

For patients whose LVEF drops to values between 40% and 45%, the decision to stop or continue ADCT-502 should be based on [Table 3](#). Additional evaluations to evaluate safety may be performed as clinically indicated.

**Table 3: Dose Modification Guidelines for Left Ventricular Dysfunction**

Symptomatic CHF	LVEF < 40% (Grade 3 or 4)	LVEF 40% to ≤ 45% and Decrease is ≥ 10% Points from Baseline (Grade 2)	LVEF 40% to ≤ 45% and Decrease is < 10% Points from Baseline (Grade 2)	LVEF > 45% (≤ Grade 2)
Discontinue ADCT-502	Do not administer ADCT-502. Repeat LVEF assessment within 3 weeks. If LVEF <40% is confirmed, permanently discontinue ADCT-502.	Do not administer ADCT-502. Repeat LVEF assessment within 3 weeks. If the LVEF has not recovered to within 10% points from Baseline, discontinue ADCT-502.	Continue treatment with ADCT-502. Repeat LVEF assessment within 3 weeks.	Continue treatment with ADCT-502.

CHF = congestive heart failure; LVEF = Left ventricular ejection fraction

## 6 Patient Population

### 6.1 Inclusion Criteria

1. Male or female age 18 years or older.
2. Refractory to or intolerant of existing therapy(ies) known to provide clinical benefit for their condition.
3. Eastern Cooperative Oncology Group (ECOG) performance status:
  - a. Part 1: 0-2
  - b. Part 2: 0-1
4. Availability of formalin-fixed paraffin-embedded (FFPE) tumor tissue block (or unstained slides (minimum 7; 10 preferred) if block is not available) to demonstrate HER2 expression.

**Note:** any biopsy since initial diagnosis is acceptable, but if several are available, the most recent sample is preferred.

5. Pathologic diagnosis of solid tumor malignancy that is locally advanced or metastatic at time of Screening:

#### **Part 1 (Dose Escalation):**

Advanced solid tumors with documented HER2 status of IHC  $\geq 1+$  or HER2

amplified/mutated by FISH or NGS (refer to [Section 4.2](#) and [Appendix 18.3](#)).

**Note:** Clinical pathology report of HER2 status must be available for review to confirm eligibility in Part 1.

**Part 2 (Dose Expansion):**

HER2-high\* or HER2-low\*\* advanced solid tumor belonging to one of the pre-specified indications for groups A – E (breast cancer, gastric & gastroesophageal cancer, bladder cancer, non-small cell lung cancer) or one of the eight pre-specified indications for the basket group (SCLC, CRC, pancreatic, biliary tract, prostate, ovarian, endometrial, or salivary gland) according to assigned treatment group for which HER2 status has been confirmed prospectively (HER2-high or HER2-low) for study entry.

\* A HER2-high patient is defined as IHC 3+, or IHC 2+ with FISH amplification.

\*\* A HER2-low patient is defined as IHC 1+, or IHC 2+ without FISH amplification.

Note: A patient with IHC 0 / IHC 1+ with amplification is HER2-high for study purposes; a patient with IHC 3+ with negative amplification results is HER2-low for study purposes.

6. **Part 2/Dose Expansion Only:** Measurable disease as defined by Response Evaluation Criteria in Solid Tumors (RECIST) version 1.1.

Note: Lytic bone lesions or mixed lytic-blastic lesions, with identifiable soft tissue components, that can be evaluated by cross sectional imaging techniques such as CT or MRI can be considered as measurable lesions if the soft tissue component meets the definition of measurability per RECIST.

7. Screening laboratory values within the following parameters:
  - a. Absolute neutrophil count (ANC)  $\geq 1500/\text{mm}^3$  ( $\geq 1.5 \times 10^9/\text{L}$ ).
  - b. Platelet count  $\geq 100,000/\text{mm}^3$  ( $\geq 100 \times 10^9/\text{L}$ ).
  - c. Hemoglobin  $\geq 9 \text{ g/L}$  ( $\geq 5.6 \text{ mmol/L}$ ).
  - d. Aspartate transaminase (AST) and alanine aminotransferase (ALT)  $\leq 2.5 \times$  upper limit of normal (ULN); or  $\leq 5.0 \times$  ULN if liver metastases are present.
  - e. Total bilirubin  $\leq 1.5 \times$  ULN (or  $\leq 3 \times$  ULN, with direct bilirubin  $\leq 1.5 \times$  ULN, in patients with known Gilbert syndrome).
  - f. Serum/plasma creatinine  $\leq 1.5 \times$  ULN; or, if creatinine  $> 1.5 \times$  ULN, a measured creatinine clearance must be  $> 60 \text{ mL/min}$  as calculated by the Cockcroft and Gault equation for patient to be eligible.

8. Women of childbearing potential\* must agree to use a highly effective\*\* method of contraception from the time of giving informed consent until at least 16 weeks after the last dose of ADCT-502. Men with female partners who are of childbearing potential must agree that they or their partners will use a highly effective method of contraception from the time of giving informed consent until at least 16 weeks after the patient receives his last dose of ADCT-502.

\*Defined as: Sexually mature women who have not undergone bilateral tubal ligation, bilateral oophorectomy, or hysterectomy; or who have not been postmenopausal (i.e., who have not menstruated at all) for at least 1 year.

\*\*Defined as: Hormonal contraceptives (oral, injectable, patch, intrauterine devices), male partner sterilization, or total abstinence from heterosexual intercourse, when this is the preferred and usual lifestyle of the patient. **Note:** The double-barrier method (e.g., synthetic condoms, diaphragm, or cervical cap with spermicidal foam, cream, or gel), periodic abstinence (such as calendar, symptothermal, post-ovulation), withdrawal (coitus interruptus), lactational amenorrhea method, and spermicide-only are not acceptable as highly effective methods of contraception.

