-  If possible, collection of pharmacokinetic (PK), soluble HER2, and anti-drug antibodies (ADA) samples will take place at the follow-up visit 12 weeks after the last dose of ADCT-502, unless a new anticancer treatment has been initiated.
-  After completion of 6 treatment cycles, the Day 8 visit is not required unless clinically indicated.
-  A signed and dated Institutional Review Board (IRB) /Independent Ethics Committee (IEC) approved informed consent form (ICF) obtained prior to performing any study evaluations. Results (e.g., from laboratory tests or radiographic evaluations, etc.) obtained prior to the date of informed consent, but within the allowed timeframe for Screening may be used for determination of patient eligibility only if obtained as part of the patient's standard of care. Patients must meet entry criteria at Screening, and should continue to meet entry criteria at Cycle 1 Day 1 pre-dose. However, clinically acceptable variations, if they are in the opinion of the Investigator not compromising patient safety, may be allowed on that day.
-  Demography includes collection of date of birth, sex, and race.
-  Medical/Cancer history to include a complete history of all surgeries, significant diagnoses, and all cancer treatments. Results of testing for genetic abnormalities associated with the patient's tumor type (such as BRCA1, for example) will be recorded.
-  During Part 1, ship tissue sample to the central laboratory for **retrospective analysis of HER2**. An FFPE block (or slides) from any biopsy since initial diagnosis is acceptable, but if several are available, the most recent sample is preferred. Either tumor tissue block or freshly cut unstained slides (minimum 7; 10 preferred) is acceptable. During Part 2, ship tissue sample to the central laboratory for **prospective analysis of HER2** to confirm eligibility.
-  Physical examinations will include a complete review of body systems. Investigators should be cognizant of potential toxicities for ADCT-502 and similar compounds as described in the Investigator's Brochure (IB) and refer unexplained findings or abnormalities to a specialist accordingly (e.g., ocular toxicity to an ophthalmologist, etc.).
-  A physical examination does not need to be repeated if performed within 72 hours prior to Day 1 of any cycle.

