- The recommendation of G-CSF use in case of (febrile) neutropenia was revised for clarification with additional reference to ASCO guidelines, Section 5.2.
- Inclusion criterion 4 was further clarified to provide more accurate information on the tumor tissue that is expected to be received for demonstrating HER2 expression. The number of slides had to be increased in case retesting is needed. The SoE Table 1 was revised accordingly.
- The unit of creatinine clearance was corrected in Inclusion criterion 7.
- Exclusion criterion 15 was revised for clarification.
- Prophylaxis with dexamethasone (Section 9.1), recommendations for treatment of edema and/or pleural effusion (Section 9.5), and other supportive care (Section 9.6) were added based on emerging safety data of other investigational agents containing the same pyrrolobenzodiazepine warhead.
- ECG will be recorded in triplicate in order to more robustly investigate the ECG-PK relationship. Associated instructions, e.g., sequence of assessments, are provided in SoE Table 1 and Table 2, Section 10.1, and 10.4.1.
- Section 10.3 indicates that imaging central review will be used.
- Sections 10.3, 10.4, and 10.4.2 were revised to include the instructions already present in footnotes of the SoE Table 1.
- PK, soluble HER2, and ADA samples will not be collected beyond starting new anticancer treatment due to practicality issues, e.g., when patients would enter a new oncology clinical study, SoE Table 1 and Section 10.4.2.
- In order to prevent stability issues with PK samples, the storage temperature has been set strictly to  $\leq -70^{\circ}\text{C}$ , Section 10.5.
- Revised instruction for AE reporting in Section 11.1 to start from ICF signature for consistency with Section 11.2.
- Additional dose levels (150 and 210 mg) have been implemented in the mCRM, Table 9 of Appendix 18.4. Therefore, the number of dose levels has not been limited to 10 in the statistical model in 18.4.2, and Figure2 and the graphical representations of Scenarios 1 to 5 have been updated.

In addition, administrative and editorial changes have been performed and revisions to the protocol text have also been applied to the synopsis section.

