#### **4.8.3 Laboratory Data**

Laboratory data of hematology, chemistry, and coagulation will be reported in SI units.

All results will be summarized using shift from baseline. Shifts for clinical laboratory results that can be graded according to CTCAE version 4.0 will be summarized by CTCAE grade.

Laboratory data, including urinalysis will be listed. Pregnancy test results will not be listed, but will be included in datasets.

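### Inclusion criterion 7c prints the haemoglobin entry limit as two values that differ tenfold (9 g/L and 5.6 mmol/L); 9 g/dL was evidently meant.

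*Protocol*

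**What the plan says.** Criterion 7 lists the laboratory values required at Screening. Item 7c reads "Hemoglobin $\geq 9 \text{ g/L}$ ( $\geq 5.6 \text{ mmol/L" (the second limit is the bracketed one). The wording is the same in the Synopsis and in Section 6.1. Unlike criterion 6, criterion 7 is not restricted to Part 2, so it governed entry to Part 1.

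The two items before it have the same layout, a limit followed by a bracketed restatement in another unit. For platelets, 7b reads "Platelet count $\geq 100,000/\text{mm}^3$ ( $\geq 100 \times 10^9/\text{L".

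Footnote 3 to the Schedule of Events (Table 1) says when the limits apply: "Patients must meet entry criteria at Screening, and should continue to meet entry criteria at Cycle 1 Day 1 pre-dose". It then allows clinically acceptable variations on that day if the investigator judges that safety is not compromised.

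The Amendment 2 summary of changes records a unit correction elsewhere in this criterion: "The unit of creatinine clearance was corrected in Inclusion criterion 7". Haemoglobin is not mentioned. No other part of the protocol or SAP gives a haemoglobin entry limit.

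**The concern.** A bracket after a limit should restate the same limit in another unit. In 7c it does not, so the criterion contains two entry limits, and only one of them works as a safety threshold. A limit of 9 g/L is 0.9 g/dL, which practically every patient would pass.

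Haemoglobin at entry matters for how toxicity is handled later. Section 4.6.2 counts Grade 4 anaemia, and Grade 3 anaemia requiring transfusion, as dose-limiting toxicities. Section 5.2 allows dosing to resume after Grade 3 or 4 anaemia once the patient is back to Grade 1 or Baseline, so a very low entry value would also lower that recovery target. The SAP summarises laboratory results as shifts from baseline.

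There is also a practical route to a missed deviation. SAP Section 4.8.3 states: "Laboratory data of hematology, chemistry, and coagulation will be reported in SI units". If haemoglobin is held in g/L, a check programmed with the printed g/L figure would flag nobody. The documents do not say that such a check exists, so this point carries little weight.

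**Working it through.** **Inputs**
- Mass limit, criterion 7c: 9 g/L.
- Bracketed molar limit, criterion 7c: 5.6 mmol/L.
- Haemoglobin monomer mass: assumed 16.1 g/mmol, range 16.0 to 16.2. The documents do not give it.

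**Step 1. Do the neighbouring brackets restate their limits?** One mm³ is 10⁻⁶ L.
- 7a: 1,500 / 10⁻⁶ L = 1.5 × 10⁹/L, as printed.
- 7b: 100,000 / 10⁻⁶ L = 100 × 10⁹/L, as printed.

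Both are exact, so 7c should be read as one limit in two units.

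**Step 2. Try to reproduce the 7c bracket from 9 g/L.** Formula: mmol/L = (g/L) / (g/mmol).
- 9 / 16.1 = 0.559 mmol/L (9 / 16.2 = 0.556; 9 / 16.0 = 0.563).

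The printed 5.6 is not reproduced.

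**Step 3. Convert the bracket back.** Formula: g/L = (mmol/L) × (g/mmol).
- 5.6 × 16.1 = 90.2 g/L (5.6 × 16.0 = 89.6; 5.6 × 16.2 = 90.7).
- Ratio to the printed mass limit: 90.16 / 9 = 10.02 (89.6 / 9 = 9.96; 90.72 / 9 = 10.08).

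**Step 4. Test 9 g/dL as the intended value.** 9 g/dL = 90 g/L.
- 90 / 16.1 = 5.59 mmol/L (90 / 16.2 = 5.56; 90 / 16.0 = 5.63).

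This rounds to the printed 5.6 throughout the range.

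**Step 5. Does the answer depend on the assumed mass?**

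| Assumed mass (g/mmol) | 9 g/L in mmol/L | 9 g/dL in mmol/L | 5.6 mmol/L in g/L | Ratio of the two printed limits |
|---|---|---|---|---|
| 16.0 | 0.563 | 5.63 | 89.6 | 9.96 |
| 16.1 | 0.559 | 5.59 | 90.2 | 10.02 |
| 16.2 | 0.556 | 5.56 | 90.7 | 10.08 |
| 17.0 (deliberately wide) | 0.529 | 5.29 | 95.2 | 10.58 |
| 64.458 (tetramer) | 0.140 | 1.40 | 361 | 40.1 |

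For 9 g/L to equal 5.6 mmol/L, the mass would have to be 9 / 5.6 = 1.61 g/mmol, about a tenth of the monomer mass. No basis in the table comes near that. On the tetramer basis neither 9 g/L nor 9 g/dL gives 5.6, so the bracket was evidently computed per monomer.

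**The case against.** The strongest reply is that the line corrects itself. The bracket gives a usable limit, 9 g/L is recognisable as a misprint, and a site would read 9 g/dL. Nothing in the documents shows that anyone applied the literal figure or that an ineligible patient was enrolled. This stands, and it limits the likely harm. It does not make the printed criterion correct.

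The route through the SAP is hypothetical. The SAP plans no eligibility check and no protocol-deviation analysis, and it does not say which SI unit it uses for haemoglobin. If that unit is mmol/L, the bracketed value is the one a check would use. This stands too.

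An effect on anaemia dose-limiting toxicities or on the dose-escalation model is unlikely. Section 4.6.2 leaves out events clearly due to underlying disease or extraneous causes, exclusion criterion 19 bars other severe or uncontrolled conditions, and the steering committee reviews all available safety data before it confirms each dose. The SAP tests no hypotheses.

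Part 2 was not performed (SAP Section 3.3), so an edit to the criterion can no longer change enrolment. That moves the useful action to the study report and a look at the Part 1 data, but does not remove it.

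Finally, the claim that 9 g/dL rounds to 5.6 holds for 16.0 to 16.2 g/mmol but not at 17.0, where it gives 5.29. The tenfold gap holds in either case.

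**Conclusion.** The concern holds. Criterion 7c is wrong as printed in both places: its two limits differ by a factor of 10.0 (9.96 to 10.08 for a monomer mass of 16.0 to 16.2 g/mmol, and up to 10.58 at 17.0). The only outside input is that mass, and the conclusion does not depend on its exact value. That 9 g/dL was intended is an inference, though a strong one: it reproduces the bracket, and the literal 9 g/L is not a workable entry limit.

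This should be fixed because it is an operative safety threshold in a first-in-human trial. It is not a design or analysis error.

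**What to change.** Change 7c in the Synopsis and in Section 6.1 to: haemoglobin ≥ 9 g/dL (≥ 90 g/L; ≥ 5.6 mmol/L), with the sponsor confirming that this was the limit intended.

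State the corrected limit in the study report and compare Part 1 entry haemoglobin with 90 g/L, using the laboratory listings already planned in SAP Section 4.8.3. Look at the Screening value as well as the analysis baseline: SAP Section 4.8 takes baseline as the last non-missing value up to first dose, which may be the Cycle 1 Day 1 sample, when some variation was allowed. If an eligibility check was programmed, confirm which value and unit it used.

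The cost is a one-line correction in two places and one pass through a listing. Design and analysis are unaffected.

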## 6.2 Exclusion Criteria

1. Known history of  $\geq$  Grade 3 hypersensitivity to a therapeutic antibody.
2. Known history of positive serum human ADA to trastuzumab.
3. History of Stevens-Johnson syndrome or toxic epidermal necrolysis syndrome.
4. Major surgical procedure or significant traumatic injury, radiotherapy, chemotherapy, targeted therapy, hormone therapy (except for luteinizing hormone-releasing hormone (LHRH) agonists or denosumab) or other anticancer therapy within 21 days OR within 5 half-lives of the product, whichever is shorter, prior to the Cycle 1, Day 1 visit.

**Note:** cumulative dose of anthracycline  $>450 \text{ mg/m}^2$  is prohibited.

5. Failure to recover to Grade 0 or Grade 1 from acute non-hematologic toxicity due to previous therapy, prior to screening (with the exception of alopecia).
6. Central Nervous System (CNS) disease only.
7. Symptomatic CNS metastases or evidence of leptomeningeal disease (brain MRI or previously documented cerebrospinal fluid (CSF) cytology).

Previously treated asymptomatic CNS metastases are permitted provided that the last treatment (systemic anticancer therapy and/or local radiotherapy) was completed  $\geq 8$  weeks prior to Day 1 except usage of low dose of steroids on a taper (i.e. up to 10 mg on Day 1 and consecutive days is permissible if being tapered down). Patients with discrete dural metastases are eligible.

8. Active cardiac disease including any of the following:
    - Angina pectoris that requires the use of anti-anginal medication.
    - Ventricular arrhythmias except for benign premature ventricular contractions.
    - Supraventricular and nodal arrhythmias requiring a pacemaker or not controlled with medication.
    - Clinically significant valvular disease with documented compromise in cardiac function.
    - Symptomatic pericarditis.
    - Congenital long QT syndrome or a corrected QTc interval  $\geq 450$  ms at Screening.
    - LVEF  $< 50\%$  at Screening or a history of decrease in LVEF to  $< 40\%$  during previous treatment with HER2 targeted therapy.
  9. History of clinically significant cardiovascular dysfunction including any one of the following:
    - History of myocardial infarction (MI) or recent MI documented by elevated cardiac enzymes or persistent regional wall abnormalities on assessment of left ventricular function within 6 months prior to Day 1.
    - History of documented congestive heart failure (New York Heart Association functional classification III-IV).
    - Documented cardiomyopathy.
    - Uncontrolled hypertension (systolic blood pressure  $> 180$  mm Hg or diastolic blood pressure  $> 100$  mm Hg).
  10. Active ulceration of the upper gastrointestinal tract or gastrointestinal bleeding.
  11. Active autoimmune disease, motor neuropathy considered of autoimmune origin, and other CNS autoimmune disease.
  12. Patients receiving concomitant immunosuppressive agents or chronic corticosteroids use, at study entry except in cases outlined below:
    - a. Topical applications (e.g. rash), inhaled sprays (e.g. obstructive airways diseases), eye drops or local injections (e.g. intra-articular), or as physiologic replacement are permitted.
  13. Known human immunodeficiency virus (HIV) infection; known seropositive for hepatitis B surface antigen (HBsAg), or antibody to hepatitis C virus (anti-HCV) with confirmatory testing and requiring anti-viral therapy.
- Note:** Testing is not mandatory to be eligible. Testing for HCV should be considered if the patient is at risk for having undiagnosed HCV (e.g., history of injection drug use).

14. Any other malignancy within 3 years prior to Day 1, with the exception of adequately treated in-situ carcinoma of the cervix uteri, basal or squamous cell carcinoma or other non-melanomatous skin cancer.
15. Active bleeding diathesis or significant anticoagulation (such as with oral anti-vitamin K medication. Low-dose warfarin, aspirin, or equivalent, are permitted as long as the INR  $\leq 2.0$ ).
16. History of thromboembolic or cerebrovascular events within the last 6 months, including transient ischemic attack, cerebrovascular accident, deep vein thrombosis or pulmonary embolism.
17. Clinically significant third space fluid accumulation (i.e., ascites requiring tap or pleural effusion that is either requiring tap or associated with shortness of breath).
18. Breastfeeding or pregnant.
19. Other concurrent severe and/or uncontrolled medical conditions (e.g., uncontrolled diabetes mellitus, active untreated or uncontrolled infection including viral and systemic fungal infections, chronic obstructive or chronic restrictive pulmonary disease including dyspnea at rest from any cause) that could cause unacceptable safety risks or compromise compliance with the protocol.

